3.2 Secondary Objective(s) & Hypothesis(es)

- (1) **Objective:** To demonstrate that administration of V501 induces non-inferior geometric mean titers (GMTs) for serum anti-HPV 6, 11, 16 and 18 at 4 weeks post dose 3 in Japanese boys aged 9- to 15-year-old compared with those in Japanese men aged 16- to 26-year-old in Phase III study (Protocol 122) for V501 at 4 weeks post dose 3.

Hypothesis: V501 generates anti-HPV 6, 11, 16 and 18 GMTs 4 weeks post dose 3 in Japanese boys aged 9- to 15-year-old that are non-inferior to those in Japanese men aged 16- to 26-year-old. (The statistical criterion for success requires that the lower bound of two-sided 95% confidence interval of GMT ratio between boys enrolled in V501-200 and men enrolled in the Phase III study V501-122 be greater than 0.5 for each HPV type.)

- (2) Objective: To describe the persistence of the serum antibody titers for the vaccine HPV types 24 months following the third dose of V501.
- (3) Objective: To estimate the immune response for the vaccine HPV types (6, 11, 16 and 18) at 4 weeks post dose 3 using GMTs.

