6.0 TRIAL FLOW CHART

Trial Period:	Period I				Period II	
Visit Number:	1	2	3	4	5	6
Scheduled Day/Month :	Day 1	Month 2	Month 6	Month 7	Month 18	Month 30
Visit Window ¹ :		2 months after Day 1 ± 3 weeks	6 months after Day 1 ± 4 weeks	3 to 7 weeks after Month 6	18 months after Day 1 ± 4 weeks	30 months after Day 1 ± 4 weeks
Administrative Procedures						
Informed Consent/Assent ²	X					
Informed Consent for Future Biomedical Research	X					
Inclusion/Exclusion Criteria	X					
Subject Identification Card	X					
Medical History	X					
Update Medical History (New condition not already recorded as medical history or adverse experiences)		X	X	X	X	X
Concomitant Medication and Non Study Vaccination Review ³	X	X	X	X	X	X
Assign Screening and Randomization/Treatment number	X					
Clinical Procedures/Assessments						
Vital Signs (oral temperature, height, weight, sitting pulse, blood pressure, and respirations) ⁴	X	X	X			
Provide Vaccination Report Card (VRC)	X	X	X			
Review and collect VRC data		X	X	X		
V501 Administration ⁵	X	X	X			
Adverse Events Monitoring	X	X	X	X	X	X
Laboratory Procedures/Assessments						
Serum for Anti-HPV antibody testing (including retention serum) ⁶	X			X	X	X
Blood (DNA) for Future Biomedical Research ⁷	X					

 To calculate visit windows, assume 1 month equals 30 days and 1 week equals 7 days. Written assent of the subject himself is to be obtained as far as possible. See section 7.1.1.5 of the protocol for details for prerequisites for medications and non-study vaccines If the subject has a fever (defined as an oral temperature of $\geq 37.5^{\circ}\text{C}$) within the 24-hour period prior to receiving a study vaccination, the subject should not receive study vaccine, and the vaccination visit should be rescheduled until after the fever has resolved. Vital sign should be measured prior to each vaccination. Height and weight are measured at Visit 1 only. Observe subjects for 30 minutes after each vaccination for immediate untoward effects. Serum for anti-HPV measurements must be collected before vaccination. Informed consent for future biomedical research samples must be obtained to collect the DNA sample. 						

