7.1.4 Other Procedures

7.1.4.1 Withdrawal/Discontinuation

When a subject discontinues/withdraws from participation in the trial, all applicable activities scheduled for the next trial visit should be performed at the time of discontinuation. Any adverse events which are present at the time of discontinuation/withdrawal should be followed in accordance with the safety requirements outlined in Section 7.2 - Assessing and Recording Adverse Events .

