8.0 STATISTICAL ANALYSIS PLAN

This section outlines the statistical analysis strategy and procedures for the study. Changes to analyses made after the protocol has been finalized, but prior to final database lock, will be documented in a supplemental SAP (sSAP) and referenced in the Clinical Study Report (CSR) for the study. Post hoc exploratory analyses will be clearly identified in the CSR.

The immunogenicity and safety analysis of Day 1 through Month 7 will be performed after the data through Month 7 have been declared final and complete. The analysis of Month 18 through Month 30 immunogenicity and safety data will take place at the end of the study. The results of this study will be summarized in 2 separate reports. The first report is the CSR including the immunogenicity and safety results based on the data through Month 7. The second one is an update to the CSR, including persistence of immune response and safety results through the end of the study.

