8.4.1 Immunogenicity Endpoints

The primary immunogenicity endpoints are seroconversion percentages to HPV 6, 11, 16 and 18 by 4 weeks post dose 3. Seroconversion is defined as changing serostatus from seronegative to seropositive. A subject with a competitive Luminex Immunoassay (cLIA) titer at or above the serostatus cutoff for a given HPV type is considered seropositive for that HPV type. The key secondary immunogenicity endpoints include cLIA geometric mean titers (GMTs) to HPV 6, 11, 16 and 18 at 4 weeks post dose 3. Other secondary endpoints include both cLIA GMTs and seroconversion percentages for each vaccine HPV type at Months 18 and 30 to assess persistence of immune responses.

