8.5 ANALYSIS POPULATION

8.5.1 Immunogenicity Analysis Populations

Per Protocol Immunogenicity (PPI) Population

The Per Protocol Immunogenicity (PPI) population will serve as the primary population for the analysis of immune response to each of the 4 HPV types (6, 11, 16 and 18). To be included in this population, subjects must:

- (1) Have received all 3 vaccinations with the correct dose of the correct clinical material, and each vaccination visit must occur within acceptable day ranges (See [Table 3](#) for acceptable day ranges for vaccination visits).
- (2) Have provided Month 7 serology result within 21 to 49 days post dose 3.
- (3) Be seronegative to the appropriate HPV type at Day 1 (See [Table 4](#) for acceptable day ranges for serum samples at Day 1).
- (4) Have no other protocol violations that could interfere with the evaluation of subject's immune response to the study vaccine.

To be included in the PPI population for HPV 6 or 11, subjects must be seronegative to both HPV 6 and 11 at Day 1. To be included in the PPI population for any other vaccine HPV type, subjects need to be seronegative at Day 1 only for the HPV type being analyzed. The final determination on protocol violations, which will be used for determining the Per-Protocol Immunogenicity population, will be made prior to the database lock and will be documented in a separate memo.

Table 3 Acceptable Day Ranges for Vaccination Visits

Dose of 4-Valent HPV L1 VLP Vaccine Scheduled for Injection	Protocol Specified Visit Window	Day Range for Inclusion in Statistical Analysis (Relative to Day 1 [†])
Dose 1	Day 1 [†]	0
Dose 2	Month 2 ± 3 weeks	36 to 84
Dose 3	Month 6 ± 4 weeks	148 to 218
[†] Day 1 refers to the date when dose 1 of 4-valent HPV L1 VLP vaccine is injected.		

Table 4 Acceptable Day Ranges for Collection of Serum Samples

Study Visit	Sample Type	Target Collection Day (Relative to Day 1 [†])	Day Range for Inclusion in Statistical Analysis (Relative to Day 1) [†]
Day 1	Serum	0	-14 to 0
Month 7	Serum	30 days post dose 3	21 to 49 post dose 3
Month 18	Serum	548	366 to 730
Month 30	Serum	913	731 to 1004
[†] Day 1 refers to the date when dose 1 of 4-valent HPV L1 VLP vaccine is injected. For Month 7, indicated target collection/day range is relative to date of injection of dose 3 of 4-valent HPV L1 VLP vaccine.			

All Type-Specific Naïve Subjects with Serology (ANSS) Population

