where GMT_1 represents the GMTs at Month 7 in the 9- to 15-year-old boys and GMT_2 represents the GMTs at Month 7 in the 16- to 26-year old young men. The test above will be performed using an analysis of variance model with a response of log-transformed individual titers and a fixed effect for age group. The statistical criterion requires that the lower bound of two-sided 95% confidence interval of GMT ratio (9- to 15-year-old boys divided by 16- to 26-year-old young men) be greater than 0.5 for all 4 HPV types. For exploratory purposes, 95% confidence interval for the difference (9- to 15-year-old boys minus 16- to 26-year-old young men) in seroconversion percentages by 4 weeks post dose 3 for each of the vaccine HPV types will be constructed. The calculation will be based on the method proposed by Miettinen and Nurminen (1985).

Persistence of immune responses

Anti-HPV 6, 11, 16 and 18 GMTs and seroconversion percentages at Months 18 and 30 will be summarized in the PPI population to assess the persistence of immune responses. Longitudinal plots of the GMTs from Day 1 through Month 30 will also be provided for graphical display.

[Table 5](#) summarizes the immunogenicity analyses.

Table 5 Analysis Strategy for Immunogenicity Variables

Endpoints	Variable	Primary /secondary /supportive	Margin	PPI	ANSS	Point estimate and 95% CI
Immune Response at 4 weeks post dose 3						
Seroconversion percentage to HPV 6, 11, 16 and 18 by 4 weeks post dose 3 (each type will be analyzed separately)	Seroconversion percentage by 4 weeks post dose 3	Primary	N/A	•	•	•
Anti-HPV 6, 11, 16 and 18 Titer at 4 weeks post dose 3 (each type will be analyzed separately)	GMT at 4 weeks post dose 3	Secondary	N/A	•	•	•
Comparison of immune response between 9- to 15- year-old boys and 16- to 26-year-old young men						
Anti-HPV 6, 11, 16 and 18 Titer at 4 weeks post dose 3 (each type will be compared separately)	Ratio of GMT at 4 weeks post dose 3 (9- to 15- year-old boys divided by 16- to 26- year-old men)	Secondary	2- fold (0.5)	•		•
Seroconversion percentage to HPV 6, 11, 16 and 18 by 4 weeks post dose 3 (each type will be summarized separately)	Difference in seroconversion percentage by 4 weeks post dose 3 (9- to 15- year-old boys minus 16- to 26-year-old men)	Supportive	Not determined	•		•
Persistent Immune response						
Anti-HPV 6, 11, 16 and 18 Titer at each time point (each type will be compared separately)	GMT at each time point	Secondary	N/A	•		•

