8.11 COMPLIANCE (MEDICATION ADHERENCE)

Compliance is defined in this study as receipt of all scheduled study vaccinations. To summarize compliance, the numbers of subjects who receive each vaccination will be tabulated. Compliance with the planned vaccination schedule (Day 1, Month 2, Month 6) will be described by histograms of actual intervals between vaccinations relative to the expected interval.

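### Do the Month 18 and Month 30 serum ranges in Table 4 need to be re-timed from dose 3, with a rule for duplicate sera?

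*Combined protocol and SAP*

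**What the plan says.** Section 3.2 gives the second secondary objective: "To describe the persistence of the serum antibody titers for the vaccine HPV types 24 months following the third dose of V501". Section 8.4.1 turns this into endpoints at nominal visits, namely GMTs and "seroconversion percentages for each vaccine HPV type at Months 18 and 30 to assess persistence of immune responses". Section 8.6.1 reports them descriptively in one population: GMTs and "seroconversion percentages at Months 18 and 30 will be summarized in the PPI population to assess the persistence of immune responses".

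The flow chart in Section 6.0 schedules both visits from Day 1, each within 4 weeks either side, under this convention: "To calculate visit windows, assume 1 month equals 30 days and 1 week equals 7 days".

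Table 4 in Section 8.5.1 then sets the days that count for analysis. For Month 18 these are Days 366 to 730 (target 548), and for Month 30 Days 731 to 1004 (target 913), both from dose 1. One visit has another origin: "For Month 7, indicated target collection/day range is relative to date of injection of dose 3 of 4-valent HPV L1 VLP vaccine".

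When a boy withdraws, Section 7.1.4.1 asks that "all applicable activities scheduled for the next trial visit should be performed at the time of discontinuation". Section 8.11 says that adherence to the vaccination schedule "will be described by histograms of actual intervals between vaccinations relative to the expected interval". It plans no matching display for serum timing, and no section says which serum is used if two fall in one range.

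**The concern.** The objective and the analysis range start their clocks at different doses, and the ranges are several times wider than the visits they serve. A serum taken well short of 24 months after dose 3 could be reported as Month 30. If titers wane, such sera would make persistence look better than it is.

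The plan also creates off-schedule sera, because withdrawal triggers the next visit's blood draw. Suppose a boy is bled on schedule at Month 18 and withdraws on Day 700. Assigned by day, his second serum is another Month 18 serum. Assigned by visit label, it is a Month 30 serum outside its range. Two analysts could treat him differently, and no planned table would show a reader how far the sera lie from the stated time point. Persistence is a named secondary objective and the main immunogenicity output of Period II.

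**Working it through.** **Inputs.** Section 6.0: 30-day months; dose 3 at Month 6 ± 28 days; Months 18 and 30 ± 28 days. Table 3: dose 3 accepted on Days 148 to 218. Table 4: ranges and targets as above.

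**The plan's own targets.** 18 × 365.25/12 = 547.9 and 30 × 365.25/12 = 913.1, so 548 and 913 reproduce with calendar months. The flow chart's convention gives 540 and 900. The gap of 8 and 13 days is harmless, since both sets lie well inside the ranges.

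**Widths (inclusive).** Month 18: 730 − 366 + 1 = 365 days. Month 30: 1004 − 731 + 1 = 274 days. Flow-chart windows are Days 512 to 568 and 872 to 928, each 57 days.

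**Days since dose 3**

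| Case | Month 18 | Month 30 |
|---|---|---|
| Flow chart kept (dose 3 on Days 152–208) | 512−208 = 304 to 568−152 = 416 | 872−208 = 664 to 928−152 = 776 |
| Visit on schedule, any Table 3 dose 3 | 512−218 = 294 to 568−148 = 420 | 872−218 = 654 to 928−148 = 780 |
| Table 4 limits, dose 3 on Day 180 | 366−180 = 186 to 730−180 = 550 | 731−180 = 551 to 1004−180 = 824 |
| Table 4 limits, any Table 3 dose 3 | 366−218 = 148 to 730−148 = 582 | 731−218 = 513 to 1004−148 = 856 |

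Boys on schedule give their Month 30 serum at 664/30 = 22.1 to 776/30 = 25.9 months. The dose 1 origin adds only about ±35 days, half the width of the Table 3 range for dose 3. The rest of the spread comes from range width and needs an off-schedule draw.

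**Where the assignment is ambiguous.** Take a withdrawal draw in Period II:

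- Before Day 366: labelled Month 18 and outside its range, so excluded on either reading.
- Day 366 up to the Month 18 visit: Month 18 on either reading.
- After the Month 18 visit up to Day 730: a second Month 18 serum by day, or an excluded Month 30 serum by label.
- Day 731 up to the Month 30 visit: Month 30 on either reading.

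Among withdrawal draws, only the third interval leaves a choice.

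**Size at Month 30.** Assume 5 to 10% of boys withdraw evenly over 900 days and titers fall 1.5- to 3-fold a year. Days 731 to 871 are 141 days.

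- Share: 141/900 × 5–10% = 0.78 to 1.57% of boys.
- Mean lead on Day 913: 913 − 801 = 112 days.
- GMT shift, exp(share × ln(fold) × 112/365.25) − 1: 0.10% (5%, 1.5-fold) to 0.53% (10%, 3-fold).

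Measured from Day 900 instead, the lead is 99 days and the shift is smaller. An extreme bound, with 5 to 10% of sera all on Day 731 (182 days early), is 1.0 to 5.6%.

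**Size at Month 18 if the wrong duplicate were used.** With the scheduled serum on Day 540, the ambiguous Days 541 to 730 are 190 days.

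- Share: 190/900 × 5–10% = 1.06 to 2.11%.
- Mean lag: 635.5 − 540 = 95.5 days.
- Shift: 1 − exp(−share × ln(fold) × 95.5/365.25) = 0.11 to 0.60%, downward.

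**Yardstick.** Section 8.9.1 plans a Month 7 GMT interval with a half-width of 0.24 on the log scale. The check is t(94 df) × 1.2/√95 = 0.244, close to the 1.27-fold stated. With a similar SD and no more boys, the Month 30 interval is at least as wide.

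**What narrower ranges would cost.** One alternative is dose-3-based ranges of 360 ± 70 and 720 ± 70 days, that is 290 to 430 and 650 to 790. These keep every on-schedule serum (294 to 420 and 654 to 780). But with dose 3 on Day 148 the Month 30 range would close on Day 148 + 790 = 938. A boy bled 11 days after the visit window ended would then leave the main summary, whereas Table 4 keeps him until Day 1004.

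**The case for a change.** The best argument for acting is that the late ranges are out of step with the rest of the plan. The per-protocol Month 7 range of 21 to 49 days equals its visit window, and the Table 3 ranges exceed the flow chart by only 3 to 10 days at each end. Months 18 and 30 alone depart by months, without explanation. Sera 513 to 582 days after dose 3 can carry either label in different boys. Persistence is analysed in one population only, so nothing would reveal a timing effect. The dose 3 date is already needed for Month 7, and Section 8.0 provides for a supplemental SAP, so an edit would be cheap.

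The facts stand, including the absence of a tie-break and of a serum-timing display. It does not stand that off-schedule sera have no rule. Table 4 is itself the rule for inclusion: a draw outside the visit window but inside the range counts, and one outside every range does not. Nor does the mismatch of origin carry much weight, since Section 8.4.1 names Months 18 and 30 as the time points and dose 3 is due at Month 6. A single serum at the range limits can be well off its target value (1.22 to 1.73 times on Day 731, 0.76 to 0.90 times on Day 1004, under the same decay assumption), but few are expected there and the two ends pull in opposite directions.

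**Conclusion.** No change is called for. The wide adjoining ranges are a fair trade-off: they keep late attenders in a trial of about 100 boys and accept looser timing for a few off-schedule sera. The missing choice between two sera is a gap that an analyst fills sensibly, for example by keeping the scheduled Month 18 serum, which lies closer to the target than a later withdrawal draw. Actual days since dose 3 can be listed from data already collected.

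The expected effect is about 0.1 to 0.5% on the Month 30 GMT. Even if the wrong duplicate were used, the effect is about 0.1 to 0.6% on the Month 18 GMT. The planned interval is roughly 27% each way at Month 7. These sizes rest on assumed decay and withdrawal rates that the documents do not give, and they leave out late or rescheduled visits, whose number cannot be known from the plan. The net direction of error is not established. The primary and non-inferiority analyses use Month 7 sera, already timed from dose 3, so no success criterion, power figure or error rate depends on this point.

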8.5.2 Safety Analysis Populations

All subjects who received at least 1 study vaccination and have follow-up data will be included in the analysis of safety.

8.6 STATISTICAL METHODS

Statistical testing and inference for safety analyses are described in 8.6.2. Immunogenicity results that will be deemed to be statistically significant after consideration of the Type I error control strategy are described in Section 8.8, Multiplicity. Nominal p-values may be computed for other immunogenicity analyses, but should be interpreted with caution due to potential issues of multiplicity, sample size, etc. Unless otherwise stated, all statistical tests will be conducted at the $\alpha=0.05$ (2-sided) level.

8.6.1 Statistical Methods for Immunogenicity Analyses

This section describes the statistical methods that address the primary and secondary objectives.

Estimation of seroconversion percentage

The primary immunogenicity hypothesis with respect to anti-HPV 6, 11, 16 and 18 seroconversion percentages by 4 weeks post dose 3 will be evaluated by computing point estimates and constructing 95% confidence interval. Calculation of the confidence interval is based on the exact binomial method proposed by Clopper and Pearson (1934). Success of this study requires that the point estimates of seroconversion percentage on all the 4 HPV types exceed 90%.

Estimation of GMTs

Anti-HPV 6, 11, 16 and 18 GMT at 4 weeks post dose 3 will be evaluated by computing point estimates and constructing 95% confidence interval. The values will be log-transformed before analysis. As such, the confidence intervals for the means will be constructed on the natural log scale and will reference the t-distribution. Exponentiating the means and lower and upper limits of these confidence intervals will yield estimates for the population geometric means titer and confidence intervals about the geometric means titer on the original scale.

Comparison of immune response (9-15 years old boys vs. 16-26 years old young men)

The secondary hypothesis that the immune response in 9- to 15-year-old boys is non-inferior to that in 16- to 26-year-old young men (all men who were vaccinated by V501 and met the per-protocol immunogenicity criteria of PN122) will be addressed by 95% confidence intervals based on one-sided tests (one corresponding to each HPV type) conducted at the $\alpha=0.025$ level (1-sided). For each HPV type, the hypotheses to be tested are:

$$H_0: \text{GMT}_1/\text{GMT}_2 \leq 0.5$$

$$H_1: \text{GMT}_1/\text{GMT}_2 > 0.5$$

where GMT_1 represents the GMTs at Month 7 in the 9- to 15-year-old boys and GMT_2 represents the GMTs at Month 7 in the 16- to 26-year old young men. The test above will be performed using an analysis of variance model with a response of log-transformed individual titers and a fixed effect for age group. The statistical criterion requires that the lower bound of two-sided 95% confidence interval of GMT ratio (9- to 15-year-old boys divided by 16- to 26-year-old young men) be greater than 0.5 for all 4 HPV types. For exploratory purposes, 95% confidence interval for the difference (9- to 15-year-old boys minus 16- to 26-year-old young men) in seroconversion percentages by 4 weeks post dose 3 for each of the vaccine HPV types will be constructed. The calculation will be based on the method proposed by Miettinen and Nurminen (1985).

Persistence of immune responses

Anti-HPV 6, 11, 16 and 18 GMTs and seroconversion percentages at Months 18 and 30 will be summarized in the PPI population to assess the persistence of immune responses. Longitudinal plots of the GMTs from Day 1 through Month 30 will also be provided for graphical display.

[Table 5](#) summarizes the immunogenicity analyses.

Table 5 Analysis Strategy for Immunogenicity Variables

Endpoints	Variable	Primary /secondary /supportive	Margin	PPI	ANSS	Point estimate and 95% CI
Immune Response at 4 weeks post dose 3						
Seroconversion percentage to HPV 6, 11, 16 and 18 by 4 weeks post dose 3 (each type will be analyzed separately)	Seroconversion percentage by 4 weeks post dose 3	Primary	N/A	•	•	•
Anti-HPV 6, 11, 16 and 18 Titer at 4 weeks post dose 3 (each type will be analyzed separately)	GMT at 4 weeks post dose 3	Secondary	N/A	•	•	•
Comparison of immune response between 9- to 15- year-old boys and 16- to 26-year-old young men						
Anti-HPV 6, 11, 16 and 18 Titer at 4 weeks post dose 3 (each type will be compared separately)	Ratio of GMT at 4 weeks post dose 3 (9- to 15- year-old boys divided by 16- to 26- year-old men)	Secondary	2- fold (0.5)	•		•
Seroconversion percentage to HPV 6, 11, 16 and 18 by 4 weeks post dose 3 (each type will be summarized separately)	Difference in seroconversion percentage by 4 weeks post dose 3 (9- to 15- year-old boys minus 16- to 26-year-old men)	Supportive	Not determined	•		•
Persistent Immune response						
Anti-HPV 6, 11, 16 and 18 Titer at each time point (each type will be compared separately)	GMT at each time point	Secondary	N/A	•		•
Seroconversion percentage to HPV 6, 11, 16 and 18 by each time point (each type will be summarized separately)	Seroconversion percentage by each time point	Supportive	N/A	•		•
PPI=Per protocol immunogenicity; ANSS= all type-specific naïve subjects with serology.						

The strategy to address multiplicity issues with regard to multiple immunogenicity endpoints, and/or multiple time points is described in Section 8.8, Multiplicity.

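### Does Table 5's wording of seroconversion 'by' each time point hide loss of antibody at Months 18 and 30?

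*Combined protocol and SAP*

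**What the plan says.** The persistence objective in Section 3.2 is "To describe the persistence of the serum antibody titers for the vaccine HPV types 24 months following the third dose of V501".

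Section 8.4.1 defines the event: "Seroconversion is defined as changing serostatus from seronegative to seropositive". It then places among the other secondary endpoints "both cLIA GMTs and seroconversion percentages for each vaccine HPV type at Months 18 and 30 to assess persistence of immune responses".

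The persistence paragraph of Section 8.6.1 plans that "GMTs and seroconversion percentages at Months 18 and 30 will be summarized in the PPI population to assess the persistence of immune responses", and adds: "Longitudinal plots of the GMTs from Day 1 through Month 30 will also be provided for graphical display".

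Table 5, which is introduced as a summary of these analyses, has two persistence rows. The first is ranked secondary and its variable is "GMT at each time point". The second is ranked supportive and reads "Seroconversion percentage to HPV 6, 11, 16 and 18 by each time point".

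**The concern.** Seroconversion is defined as a change of status, so having seroconverted 'by' Month 30 can mean having changed status at any sample up to then. For the primary endpoint this makes no difference, because Month 7 is the first scheduled sample after baseline and 'by' and 'at' give the same count. At Months 18 and 30 they part. A boy who was positive at Month 7 and is negative at Month 30 counts under 'by' and does not count under 'at'. The plan has no explicit rule for a boy who reverts.

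If the row were programmed literally, it could report about 99% at Month 30 however many boys had fallen below the cutoff, and a reader could take that as evidence of durable antibody. The label also differs: Section 8.4.1 puts this endpoint among the secondary ones and Table 5 calls it supportive.

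**Working it through.** **The plan's own figures.** No figure is stated for the persistence analysis. The Month 7 figures in Section 8.9.1 reproduce:

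- Probability that the point estimate exceeds 90% for one type, with 95 boys and a true rate of 95%: at least 86 of 95 must convert (86/95 = 90.5%, 85/95 = 89.5%). P(X ≥ 86) = 0.979 (stated 0.98).
- All four types, treated as independent: 0.979^4 = 0.920 (stated 0.92).
- Clopper-Pearson half-width at 90/95: 5.06 points (stated as about 5).
- GMT half-width: 1.96 × 1.2/√95 = 0.241 on the natural log scale (stated 0.24), a factor of about 1.27.

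None of these depends on 'by' or 'at' in the persistence row.

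**What the literal reading would do.** Take 94 of 95 boys converting at Month 7, all 95 sampled at Month 30, and a fraction w of converters below the cutoff by then. The documents give no loss rates, so w is an assumption. The cumulative percentage is 94/95 whatever w is. The point-in-time percentage is 94(1 − w)/95, with the count rounded to whole boys.

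| w (assumed) | 'by' Month 30 | 'at' Month 30 | Gap in points |
|---|---|---|---|
| 5% | 98.9% | 89/95 = 93.7% | 5.3 |
| 10% | 98.9% | 85/95 = 89.5% | 9.5 |
| 20% | 98.9% | 75/95 = 78.9% | 20.0 |
| 30% | 98.9% | 66/95 = 69.5% | 29.5 |

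Against a half-width of 5.06 points, the gap is about 1 to 6 half-widths. The two readings would therefore give visibly different results, and the question is which one the plan adopts.

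**Which reading the plan adopts.**

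1. The endpoint definition (Section 8.4.1) and the method paragraph (Section 8.6.1) both say 'at Months 18 and 30' for the percentage. Table 5 only summarizes that text.
2. The persistence summaries use the PPI population, which Section 8.5.1 restricts to boys seronegative at Day 1 for the type concerned (for both types in the case of HPV 6 and 11). For such a boy, having changed to seropositive at Month 30 is the same as having a titer at or above the cutoff at Month 30. The 'at' wording therefore already yields the percentage seropositive at the visit.
3. Table 4 gives Month 18 and Month 30 serum their own day ranges for inclusion, which suits a visit-by-visit summary.
4. The plan uses the two prepositions loosely. The primary endpoint is 'at' 4 weeks post dose 3 in Section 3.1 and 'by' in Section 8.4.1. Section 8.1 uses both, and in Table 5 a block headed with 'at' contains a row worded with 'by'. Nowhere is an ever-seroconverted rule stated.

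**Whether waning would be seen anyway.** The objective is about titers, and GMT at each time point is the secondary persistence variable. GMTs fall as titers fall. With 95 boys still sampled and the planned SD of 1.2, each visit's GMT has a 95% interval of about 1.27-fold either way, and the GMT plots run to Month 30.

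**The case for a change.** The strongest case for a change is that the plan gives two wordings for one endpoint and no rule of precedence. In Table 5, 'by' goes with seroconversion and 'at' with GMT, both in the 4-week single-arm rows and in the persistence rows, so a programmer working from the table alone could take the difference as intended. GMTs do not make the percentage redundant: they describe the average and do not say how many boys fall below the cutoff. The percentage is the only planned persistence measure at the level of the individual boy. The term seropositive, already defined in Section 8.4.1, would have been cleaner, and Section 8.0 allows changes in a supplemental SAP before final database lock.

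The inconsistency is real, and so is the point that GMTs and percentages answer different questions. Neither leads to a different analysis. The subject-level measure that the objection wants is the one that Sections 8.4.1 and 8.6.1 already describe. The cumulative result arises only if a summary row is allowed to override both of them.

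The label mismatch also stands, without consequence. Section 8.8 makes testing of the Month 7 GMT comparison conditional on the primary hypothesis and assigns nothing to persistence. The percentage is descriptive under either label.

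**Conclusion.** No change to the plan is needed. The row's wording is a clerical slip: literally cumulative, but contradicted by the two full-text statements that it summarizes. An analyst who follows those statements in the PPI population reports the percentage seropositive at each visit, and loss of antibody shows both there and in the secondary GMT analysis.

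The gap of about 5 to 29 points applies only if the table row overrides the text and if 5% to 30% of converters lose detectable antibody. The documents do not support the first condition and give no figure for the second. The primary seroconversion criterion, the non-inferiority comparison and every stated probability or precision figure are unaffected. The conclusion rests on the analyst reading Table 5 together with Sections 8.4.1 and 8.6.1.
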